7.2 Assessment Time Windows

Safety assessment summaries will be based on the nominal protocol-specified assessment times. NPRS scores will be based on actual collection dates/times wherever possible. If no collection date/time is available the nearest protocol specified assessment time will be used.

7.3 Exploratory Efficacy Endpoints

- Area under the curve (AUC) of subject's NPRS will be examined over various time periods, including but not limited to: AUC(0-12), AUC(12-24), AUC(24-48), AUC(24-72), AUC(24-96), AUC(24h to Week 1), and AUC(24h to Week 2).
- Mean daily opioid consumption (in morphine equivalents) over the same time periods as the AUC calculations above.
- Proportion of patients who drop out of the study due to inadequate analgesia from Day 1 to 15.
- Brief Pain Inventory-short form (BPI-SF) scores at the Day 8 (Week 1), Day 15 (Week 2) and Day 29 (Week 4) or ET clinic visits.
- Patient Global Evaluation (PGE) at the Day 8 (Week 1), Day 15 (Week 2) and Day 29 (Week 4) clinic visits.

- Investigator Global Evaluation (IGE) at the Day 8 (Week 1), Day 15 (Week 2) and Day 29 (Week 4) clinic visits.
- Time to first use of rescue medication.
- Percent of days that rescue medication was used.

7.4 Analysis Methods

Formal hypotheses testing will be not conducted. All p-values will be considered nominal in this study and no adjustments for multiplicity will be performed. All efficacy analyses will be based on the safety population.

7.4.1 AUC Outcomes

All AUC calculations will be done using the standard trapezoidal rule

$$AUC = \sum_{i=0}^x \left(\frac{NPRS_i + NPRS_{i+1}}{2} \right) * (T_{i+1} - T_i)$$

Where: $NPRS_i$ = NPRS at time i , and $(T_{i+1} - T_i)$ is the Time difference in hours between time i and time $i+1$.

Missing NPRS will be handled as discussed in Section 7.1.

AUC values will be analyzed using a 1-factor (treatment) analysis of variance (ANOVA) model with treatment as the main effect. In addition to the individual comparisons between each of the five CA-008 groups and the placebo group, the test for a linear trend across dose groups will be carried out using the scores 0, 0.5, 1.0, 2.0, 3.0 and 4.2 for the placebo group and the five active groups, respectively.

The AUC analyses will be presented in a summary table with standard summary statistics for each dose cohort and placebo as well as active vs. placebo mean differences, standard errors, confidence intervals and comparison p-values as appropriate. Comparisons of individual dose cohorts for dose response may be presented for certain secondary AUC endpoints.

Mean NPRS scores over time (in-clinic and diary) will be graphed over time by dose cohort. NPRS over time by each subject may also be displayed graphically as warranted. The individual NPRS and the computed AUC variables will be listed for all individual subjects.

7.4.2 Average Daily NPRS score of 2 daily diary assessments

The Average Daily NPRS scores will be computed for each subject using the NPRS scores recorded in the take-home diary from study days 3 – 15.

The Average Daily NPRS will be the average of the AM and PM scores within each day. If individual AM or PM NPRS scores are missing, the score that is present will be used as the daily average. If both scores are missing for any day, then that day will not have a daily average. The mean across all subjects of the average daily scores on each day will be graphed by day and

dose cohort. If rescue medication was taken within 4 hours of the AM or PM PI assessment, it will be replaced with the pre-rescue NPRS (if available) in the daily average.

The average daily NPRS scores will be analyzed using the same type of ANOVA model as described in Section 7.4.1 at each time point. In addition, actual date/time NPRS assessed over the outpatient period from T48h onward will be used to calculate AUC between 24 hours and Week 1 and between 24 and Week 2 and compared versus placebo.

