Secondary (efficacy):	
 1. Area-under-the-curve (AUC) over various time points using NPRS score (0–10), with adjustment for use of analgesic therapy/medication. 2. Mean average daily NPRS score of 2 daily diary assessments. 3. Mean daily opioid consumption (in morphine equivalents). 4. Proportion of patients who drop out of the study due to inadequate analgesia from Day 1 to 15. 5. Brief Pain Inventory-short form (BPI-SF) scores at the Day 8 (Week 1), Day 15 (Week 2) and Day 29 (Week 4) or ET clinic visits. 6. Patient Global Evaluation (PGE) at the Day 8 (Week 1), Day 15 (Week 2) and Day 29 (Week 4) clinic visits. 7. Investigator Global Evaluation (IGE) at the Day 8 (Week 1), Day 15 (Week 2) and Day 29 (Week 4) clinic visits.
Eligibility: Inclusion Criteria:	
 1. Male or female aged 18 - 65 years old, inclusive. 2. Planning to undergo a primary unilateral first metatarsal bunionectomy repair, without collateral procedures. 3. Be American Society of Anesthesiology (ASA) physical Class 1 or 2. Appendix J 4. In good health and capable of undergoing a bunionectomy under regional anesthesia. 5. No additional planned surgeries other than a bunionectomy during the

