- Physical exam: 1, 24, and 48 hours after the administration of study medication.
- ECG: 1.5 hours after the administration of study medication.
- Surgical Site assessment: 24 and 48 hours after the administration of study medication.
- Neurosensory Exam of the Foot / Great toe (bilateral): 24 and 48 hours after the administration of study medication.
- Clinical laboratory tests (chemistry/coagulation, hematology, and urinalysis): 1.5 hours after the administration of study medication.
- Blood draw for PK analysis: are at baseline (before dosing), and at 5 minutes, 15 minutes, 30 minutes, 45 minutes, and 1, 1.5, 2, 2.5, 3, 3.5, 4, 6, 8, 12, 16, 24, 36, and 48 hours after dosing.

Subjects with inadequately controlled pain may request rescue at any time. However, subjects will be encouraged to receive rescue medication only with an NPRS ≥ 4 . Additionally, subjects should be encouraged to wait at least 1 hour after completion of surgery (i.e. completion of sutures) before utilizing pain rescue medication, if possible. Pain intensity (NPRS) will be completed within 15 minutes prior to use of pain rescue medication. While in-clinic, subjects will be treated with the prescribed analgesic regimen (oxycodone 5 mg every 2 hours); however, if subjects do not get adequate analgesic relief they will be discontinued from the efficacy portion of the study. At this point, subjects will receive standard of care analgesics (which may or may not include intravenous opioids). Regardless of discontinuation status, subjects will be followed for safety. Discontinuation affects the computation of the analgesic endpoint only. From Day 3 to 15, over-the-counter standard of care analgesics may be used for management of pain. If needed for management of NPRS score of 4 or higher, oxycodone 5 - 15 mg every 4 - 6 hours.

After completing the assessments through 48 hours after study medication administration, the diary for at-home use will be reviewed and subjects will be discharged from the study center with the diary to record pain assessments and pain medication at home. Subjects will be provided routine standard of care for pain management after discharge from the study center. In their diary, subjects will assess their pain intensity once in the morning (08:00 ± 4 hours), and once in the evening (20:00 ± 4 hours) using the NPRS. Subjects will also record any medication they take to

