7 EFFICACY EVALUATION

7.1 Handling of Dropouts or Missing Data

All efforts will be made to minimize missing data. These efforts will include the following:

- Subjects are required to consent to continuous data collection even after discontinuation of study medication;
- Data collection will continue after subjects take rescue medication.

With the procedures above, it is expected that missing data will be minimal. Missing at random is expected to be a reasonable assumption for this dose-escalation study.

For subjects who take protocol allowed rescue medication a windowed last pain score carried forward (LOCF) will be used. The pre-rescue pain score will be used to impute scheduled assessments for 4 hours following the rescue use. Intermittent missing pain scores (due to subject sleeping, etc.) will not be imputed, and AUC will be calculated based on non-missing values. For subjects who drop out of the study prior to Day 15, or who are discontinued from efficacy and given SOC analgesics for inadequate pain relief, scheduled assessments will first be imputed using the worst prior pain score carried forward (WOCF) using the worst scheduled non missing pain score prior to drop out within the AUC period being calculated (e.g., if the AUC being calculated includes hours 12-24, the worst observed pain score between hours 12 and 24 will be used). As a sensitivity, the AUC will also be calculated where assessments after drop out will be imputed using LOCF, using the last scheduled non missing pain score prior to drop out.

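### The daily-average NPRS is analysed on available data only, so a subject imputed as a failure in the long AUCs is absent or as observed in the daily mean

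*SAP*

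**What the plan says.** The protocol synopsis lists "Mean average daily NPRS score of 2 daily diary assessments" second among its secondary efficacy endpoints. The endpoint list in SAP 7.3 omits it, but SAP 7.4.2 analyses it "using the NPRS scores recorded in the take-home diary from study days 3 – 15", with an ANOVA at each time point.

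SAP 7.4.2 gives three handling rules:

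- If one of the two daily scores is missing, the other stands for the day.
- "If both scores are missing for any day, then that day will not have a daily average".
- "If rescue medication was taken within 4 hours of the AM or PM PI assessment, it will be replaced with the pre-rescue NPRS", where such a score exists.

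It does not mention study drop-out or discontinuation from efficacy, and it does not refer to 7.1.

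SAP 7.1 does cover these subjects. For those who leave before Day 15, "or who are discontinued from efficacy and given SOC analgesics for inadequate pain relief, scheduled assessments will first be imputed" by carrying the worst prior score forward, "using the worst scheduled non missing pain score prior to drop out within the AUC period being calculated". The LOCF sensitivity is likewise stated for the AUC. SAP 7.4.1, on the AUC outcomes, sends the reader to 7.1 for missing scores.

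The output list in SAP 14.1 follows the same division. AUC Tables 14.2.1.1 and 14.2.1.2 and Figures 14.2.1.1 and 14.2.1.2 come in WOCF and LOCF versions. Table 14.2.2.1 and Figure 14.2.3, for the daily average, exist once each and carry no imputation label.

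**The concern.** Leaving the study, or being taken out of the efficacy portion, is often a consequence of pain. A by-day mean over whoever still has scores then improves when the worst-off subjects go. With 6 subjects per dose and 10 pooled placebo subjects, one such departure can move a group mean visibly and could change the apparent order of doses. SAP 2.2 says the trial is meant to determine the recommended dose.

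The plan is also inconsistent with itself. SAP 7.4.1 plots mean NPRS for in-clinic and diary scores, and those figures are listed with WOCF and LOCF. Figure 14.2.3 would show the same diary days without imputation, and nothing would tell the reader why the two differ. SAP 7.4.3 and 7.4.8 both count medication after efficacy discontinuation in two ways. SAP 7.4.2 is silent on the question.

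**Working it through.** The documents give no SD, effect size or power for this endpoint, so there is no stated figure to reproduce. The check is a comparison of rules, followed by an illustration of size.

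**Step 1. The same subject under the two sets of rules**

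| Subject | Daily average (SAP 7.4.2) | AUC 24h to Week 1 or Week 2 (SAP 7.4.1 with 7.1) |
|---|---|---|
| Leaves the study before Day 15 | Diary days before leaving count; no value afterwards | Scheduled scores after leaving, within the period, set to the worst in the period (LOCF as sensitivity) |
| Discontinued from efficacy, still followed | Later diary scores enter as recorded, unless within 4 hours of rescue with a pre-rescue score available | Scheduled scores after discontinuation imputed as above |

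SAP 7.4.2 itself says that outpatient scores from 48 hours onward feed these two AUCs, so the same diary days are in question. The 7.1 rule also cannot be carried over as it stands, because it takes the worst score from an AUC period and a daily average has none.

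**Step 2. Size of one omitted failure**

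Inputs: 6 per dose and 5 × 2 = 10 pooled placebo (SAP 2.2 and 3). Assumed, not in the documents: other subjects' daily mean m = 3 to 4, worst prior score w = 7 to 9.

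Mean with the failure imputed minus mean with the failure omitted = ((n − 1)m + w)/n − m = (w − m)/n.

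- Placebo, n = 10: (7 − 4)/10 = 0.3 to (9 − 3)/10 = 0.6 points.
- One dose, n = 6: (7 − 4)/6 = 0.5 to (9 − 3)/6 = 1.0 points.
- Two failures among 10 placebo subjects: 0.6 to 1.2 points.

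**Step 3. Size of one failure entered as observed**

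If a placebo subject discontinued from efficacy later records an assumed treated score s = 1 to 3, the difference from imputation is (w − s)/10: (7 − 3)/10 = 0.4 to (9 − 1)/10 = 0.8 points. This ignores the 4-hour replacement, so it is an upper illustration.

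**Step 4. How likely a failure is**

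Protocol 9.1.3 says that the in-clinic oxycodone regimen gave adequate relief to more than 90% of placebo subjects in previous studies. Read as a failure rate of at most 10%, P(at least one of 10) = 1 − 0.9^10 = 0.651. At 5% it is 0.401. At an assumed 20% it would be 0.893. No figure is given for CA-008 groups.

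**Step 5. Against the noise**

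With an assumed SD of 2.0 to 2.5, the SE of a 6 versus 10 comparison is SD × √(1/6 + 1/10) = 1.033 to 1.291. A placebo shift of 0.3 to 0.8 points is therefore 0.3/1.291 = 0.23 to 0.8/1.033 = 0.77 of an SE.

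**The case against.** Several points on the other side stand.

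- The efficacy endpoints are exploratory, and SAP 7.4 plans no formal testing and calls all p-values nominal. Drop-out for inadequate analgesia has its own analysis in SAP 7.4.4, and efficacy discontinuations appear in the disposition summary. Failures are not hidden from the report as a whole.
- An observed-data daily mean is a legitimate complement to imputed AUCs on the same diary data. Replacing it would have its own cost. If the worst score since Time 0 were carried forward, a subject discontinued on Day 1 could have 13 days of recorded diary scores (Days 3 to 15) overwritten by one early post-surgical value.
- SAP 7.1 can be read as the general missing-data section. But 7.4.2 does not cite it, its worst score is tied to an AUC period, and the daily-average outputs carry no imputation label. At best the plan is ambiguous.

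Three stronger readings are tempting, and the documents do not support them.

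- A reader might infer that discontinued subjects enter the daily mean on unrestricted analgesia with no adjustment. The documents do not describe it as unrestricted. The switch to standard-of-care analgesics is an in-clinic rule, and on Days 3 to 15 every subject may use over-the-counter analgesics, plus oxycodone for a score of 4 or more. SAP Section 3 calls the post-discontinuation analgesia rescue, so the 4-hour replacement can reach part of its effect.
- A reader might infer a bias against the drug because failures will be mainly on placebo. Protocol 13.4.5 expects frequent rescue on placebo, but neither document says where failures will fall.
- A reader might infer that drop-outs disappear from the endpoint altogether. Their diary days before leaving still count.

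**Conclusion.** The gap is real and of moderate importance. As written, the daily average is an available-case analysis, and its treatment of failures differs from that of the AUCs built on the same diary days. The effect favours whichever group loses its worst subjects, and its direction between arms cannot be stated in advance.

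One omitted failure is worth roughly 0.3 to 0.6 points in the placebo daily mean and 0.5 to 1.0 in a dose group. These sizes rest on the assumed pain scores above and on the gap persisting on the day in question; the comparison with the SE rests on an assumed SD. They show what one subject can do in groups this small and are not a forecast. The exploratory status of the endpoint argues for a second version alongside the present analysis, not for replacing it.

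**What to change.** Keep the observed-data analysis in SAP 7.4.2 and add a second version of Table 14.2.2.1 and Figure 14.2.3. Suggested wording:

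*The daily average will be presented in two versions. The first uses scores as recorded, with the pre-rescue replacement described above. In the second, AM and PM scores after study drop-out or discontinuation from efficacy, through Day 15, will be imputed by the Section 7.1 method (WOCF, with LOCF as sensitivity) before averaging. The carried score will be taken from scheduled assessments between [stated start] and the time of drop-out or discontinuation. In the second version, the rule that a day has no average applies only to intermittent gaps.*

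The start of the window must be written down, because there is no AUC period to borrow. It also has to reach back into the inpatient scores, since a subject discontinued in clinic has no earlier diary score to carry. Label each output with its method, and add the daily average to the endpoint list in SAP 7.3.

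The cost is SAP wording before sign-off and one more version of one table and one figure, with no new data. The drawback is that a carried worst score may overstate late pain, which is why both versions should be shown.

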In their take-home Diary, subjects will assess their pain intensity once in the morning (08:00 ± 4 hours), and once in the evening (20:00 ± 4 hours) using the NPRS. Subjects will also record any medication they take to treat their pain.

Subjects will return to the study center on Day 15 [± 2 days] for the following assessments:

- Subject home diary review (pain intensity and pain medication)
- Pain Intensity (NPRS)
- BPI-SF
- PGE
- IGE
- Vital signs
- Surgical Site assessment
- Neurosensory Exam of the Foot / Great toe (bilateral)
- Concomitant Medication Use
- AE Assessment

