10.4.1. Numerical Pain Rating Scale (NPRS) for Pain Intensity

The NPRS is an 11-point scale with anchors 0 (no pain) and 10 (worst possible pain) ([Appendix B](#); [Ferreira-Valente MA et al., 2011](#); [Hjermstad MJ, 2011](#)). Subjects will record the intensity of their current pain at the following times over the initial 48-hour period in a diary: at 0.25, 0.5, 0.75, 1, 2, 4, 8, 12, 16, 20, 24, 28, 32, 36, 40, 44, and 48 hours after the administration of study medication and within 15 minutes prior to use of pain medication. Subjects should be at rest for at least 10 minutes prior to completing NPRS assessments. NPRS Assessments between the hours of 00:00 and 06:00 may be skipped if the subject is sleeping; however, consecutive assessments may not be skipped, and the Hour 12, Hour 24, and Hour 48 assessments must be completed even if the subject is asleep. There will be a ± 5 minute window allowed for the collection of each pain intensity assessment in the first 4 hours after the end of surgery, after which will be a ± 15 minute window allowed.

After discharge and through Day 15, subjects will rate their pain intensity using the NPRS once in the morning (08:00 ± 4 hours) and once in the evening (20:00 ± 4 hours), and will capture an additional NPRS within approximately 15 min prior to each dose of pain medication. Subjects will also rate their pain intensity using the NPRS at the Day 8, Day 15 and Day 29/Early Termination (ET) visit.

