13.4.5. Analysis of Efficacy Measures

Efficacy variables will be summarized and analyzed.

The primary efficacy parameter is the area-under-the-curve (AUC) for NPRS scores across various time points, with adjustment for use of analgesic therapy/medication. The primary efficacy variable will be analyzed using an ANCOVA model with treatment as the main effect and baseline PI as the covariate. The overall treatment effect will be presented along with specific treatment arm differences and the two-sided 95% confidence intervals of the differences.

In this study, subjects are permitted to take rescue medication for analgesia. It is expected subjects randomized to placebo arm will take rescue medication often. During both inpatient and outpatient portions of the studies, the subjects will be instructed to record NPRS immediately prior (within approximately 15 min) to taking rescue medication.

For subjects who take rescue, the pre-rescue pain score will be used to impute scheduled assessments for 4 hours. Intermittent missing pain scores (due to subject sleeping, etc.) will not be imputed, and AUC will be calculated based on non-missing values. For subjects who drop out of the study prior to Day 15 due to Lack of Efficacy or Adverse Events, scheduled assessments may be imputed using worst prior pain score carried forward. All other subjects who drop out will have their last pain score carried forward.

Sensitivity analysis of the primary efficacy variable using different methods of imputation for rescue medication may also be performed.

Additional sensitivity analysis with different missing value imputation methods for subjects who drop out of the study may also be performed.

All imputation methods for pain intensity will be documented in the SAP.

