10 NPRS available from his/her diary, then compliance for this subject would be 27.8% ((10/36) *100). However, if subject A had discontinued the study on Day 10 (prior to Day 15), then the expected N of NPRS for this subject would be 16 (2 * (10-2)) and compliance would be 62.5 % ((10/16) *100). A summary of compliance will be provided overall and by treatment group.

Compliance with recording an NPRS prior to rescue in the diary will be calculated as the number of NPRS recorded prior to taking rescue medications divided by the number of rescue medication uses recorded.

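### SAP 7.4.2 has no rule for a post-rescue diary score when the pre-rescue NPRS was not recorded, so by default the score goes in unadjusted

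*SAP*

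**What the plan says.** SAP 7.4.2 averages the AM and PM diary scores for each of Days 3 to 15. Its rescue rule is triggered "If rescue medication was taken within 4 hours of the AM or PM PI assessment", and then "it will be replaced with the pre-rescue NPRS (if available) in the daily average". The unavailable case is not addressed, and the four-hour window has no stated direction. The same section does provide for a missing diary score ("If individual AM or PM NPRS scores are missing, the score that is present will be used as the daily average"), but that concerns the scheduled score, not the pre-rescue one.

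For the AUCs, SAP 7.1 says "The pre-rescue pain score will be used to impute scheduled assessments for 4 hours following the rescue use". Here the window clearly runs after the dose, but again nothing covers an unrecorded pre-rescue score.

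The plan expects some of these scores to be skipped. SAP section 6 states "Compliance with recording an NPRS prior to rescue in the diary will be calculated", and the result goes into Table 14.1.5. It is not linked to any analysis rule.

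On collection, protocol 10.4.1 says that after discharge and through Day 15 subjects "will capture an additional NPRS within approximately 15 min prior to each dose of pain medication". Protocol 9.1.3 and 13.4.5 and SAP 2.2 ask for the same. Protocol 7.1.7, the diary instruction for Days 9 to 15, says only "Subjects will also record any medication they take to treat their pain", whereas 7.1.6 (Days 3 to 8) adds the pre-dose score.

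On rescue use, protocol 13.4.5 says "It is expected subjects randomized to placebo arm will take rescue medication often". It also leaves the documentation of every pain-intensity imputation method to the SAP.

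**The concern.** The replacement rule exists so that pain relieved by rescue is not credited to the randomised treatment. It works only if the subject wrote down a score before the dose. Where that was skipped, the rule as written does nothing, so the adjustment is lost in the subjects and weeks with the poorest diary keeping.

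The scores concerned feed the daily-average NPRS and the AUCs that extend past discharge (24-72 h, 24-96 h, 24 h to Week 1, 24 h to Week 2), each compared with pooled placebo. If placebo subjects rescue more often, more of their scores are left low and the placebo-minus-active difference shrinks. With six subjects per dose and a dose trend to be read from these data, the handling should be fixed before unblinding rather than left to the programmer.

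**Working it through.** The plan gives no figure that depends on this rule, so there is nothing to reproduce. I traced the rule and then worked an illustration.

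**1. Does any provision cover a missing pre-rescue score?**

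| Provision | What it covers | Closes the gap? |
|---|---|---|
| SAP 7.4.2, missing AM or PM score | Absent diary score | No; the diary score is present |
| SAP 7.1, intermittent missing scores | Absent scheduled score, not imputed | No; same reason |
| SAP 7.1, four-hour rescue rule | Carries the pre-rescue score | No; there is none to carry |
| SAP 3, same-minute rule | Order of NPRS and rescue | No |
| SAP 7.1, WOCF versus LOCF | Dropout only | No |

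Protocol 13.4.5 allows sensitivity analyses with other rescue imputations, but the SAP plans none.

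**2. One subject-day.** Assume a pre-rescue score of 6, a post-rescue score of 4 and a score of 4 at the other diary time.

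- Replaced: (6 + 4)/2 = 5.0
- Post-rescue score kept: (4 + 4)/2 = 4.0
- Set to missing: the other score alone, 4.0

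With an analgesic drop *d*, keeping one affected score lowers that day's average by *d*/2.

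**3. Group level.** Let *f* be the share of diary scores within 4 h after rescue, *s* the share of those with no pre-rescue score, and *d* the drop. The bias in an arm mean is −*f* × *s* × *d*. If *s* and *d* are equal across arms, the difference shrinks by

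*d* × *s* × (*f*placebo − *f*active).

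All inputs are assumptions: *f* = 0.60 on placebo and 0.30 on active, a gap of 0.30. High values of *f* are possible: with the 4-to-6-hourly as-needed oxycodone in protocol 9.1.3, a subject dosing at that frequency is within 4 h of a dose for 4/6 = 67% to 4/4 = 100% of the time.

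| Drop *d* | *s* = 10% | 30% | 50% | 100% |
|---|---|---|---|---|
| 1 | 0.03 | 0.09 | 0.15 | 0.30 |
| 2 | 0.06 | 0.18 | 0.30 | 0.60 |
| 3 | 0.09 | 0.27 | 0.45 | 0.90 |

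**4. Direction.** With unequal skip rates the shrinkage is *d* × (0.60 × *s*placebo − 0.30 × *s*active). It is zero when active subjects skip twice as often as placebo subjects, and changes sign beyond that.

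**5. Scale.** Six active per cohort and 2 × 5 = 10 pooled placebo subjects give SE = SD × √(1/6 + 1/10). For an assumed SD of 1.5, 2.0 or 2.5 this is 0.77, 1.03 or 1.29. At a 2-point drop, shrinkage of 0.18 to 0.60 is 0.18/1.29 = 0.14 to 0.60/0.77 = 0.78 of a standard error.

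**6. AUC.** At 12-h spacing an interior score has a trapezoid weight of 12 h, so one score left 2 points low removes 2 × 12 = 24 NPRS-hours. From 24 h to Week 2 is 13 × 24 = 312 h, so this is 24/312 ≈ 0.08 points of time-averaged pain in that subject.

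**The case against.** **The SAP never says that the medicated score is kept.** A reader might infer that it does. The text is silent: a programmer could set the score to missing, or lean on the windowed carry-forward wording in SAP 7.1. This stands. The supportable statement is that no rule is given and that, by default, an unreplaced score remains. Nor will every post-rescue score be lower.

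**Protocol 7.1.7 does not switch off the pre-dose score.** A reader might infer that none will be recorded on Days 9 to 15. The documents do not support that: protocol 9.1.3, 10.4.1 and 13.4.5 and SAP 2.2 all ask for it, and 7.1.7 is merely silent. The 100% column above is therefore an outer bound.

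**The protocol's daily-average endpoint carries no rescue adjustment; only the AUC does.** That is correct, and keeping an observed score is consistent with that definition. But SAP 7.4.2 chose to adjust, and then adjusts only where the diary happens to be complete.

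**Consequences are limited and partly visible.** SAP 7.3 lists these endpoints as exploratory, 7.4 makes p-values nominal, and the primary objectives are safety and PK. Pre-rescue compliance is tabulated, and rescue and opioid use are analysed separately. This limits the severity.

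**A fallback may itself understate pain.** Rescue is tied to an NPRS of 4 or higher, so a score not followed by rescue tends to be lower than the missing one, and the subject-day above shows that setting to missing need not recover the loss. This is fair for an individual day. For the between-arm difference, a simulation with assumed drops of 1 to 3 points and skip rates of 30% to 100% had the default understating it by about 0.05 to 0.4 points, while carrying forward the latest eligible score brought it to within about 0.05 of the fully adjusted value.

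**Conclusion.** The gap is real and worth closing before database lock. SAP 7.4.2 and 7.1 rest the rescue adjustment on a self-recorded score and give no rule for its absence. By default this leaves unadjusted scores in the daily average and the post-discharge AUCs.

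The pull toward no difference depends on two conditions: more rescue on placebo, which the protocol's remark makes likely but does not quantify, and similar skip rates and analgesic drops across arms. The size is unknown. The 0.03-to-0.9-point range rests wholly on assumed drops, skip rates and rescue shares, and most of it lies below one standard error of a single-dose comparison. It is a systematic error in exploratory comparisons and does not touch the safety or PK objectives.

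**What to change.** - **SAP 7.4.2:** state that the rule applies to diary scores taken within 4 h *after* a rescue dose. Replace the availability condition with: *if no pre-rescue NPRS was recorded, use the most recent NPRS recorded before the dose that is not itself within 4 h after an earlier rescue; if there is none, set the score to missing.*
- **SAP 7.1:** add the same sentence after the four-hour imputation rule, so that the AUCs follow it too.
- **Sensitivity and reporting:** add an analysis that keeps the observed score, and report by arm how many scores were replaced, carried forward or set to missing.
- **Protocol:** reconcile 7.1.7 with 9.1.3 and 10.4.1 on the pre-dose NPRS for Days 9 to 15.

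The SAP changes cost a few sentences, a short derivation and one extra table, and need no new data. The downside is that some scores are carried forward or lost, more of them in frequent rescuers. With the shares assumed above and 30% skipping, the fallback would apply to 0.60 × 0.30 = 18% of placebo and 0.30 × 0.30 = 9% of active diary scores, which is why the counts by arm are needed.
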